6.1.4.1 Tumor Lysis Prophylaxis (All Subjects)

There is a potential for TLS in subjects, affected by hematologic malignancies especially in those with bulky disease, elevated pretreatment Lactate Dehydrogenase (LDH) levels, elevated leukocyte count, renal dysfunction, and dehydration. To mitigate the risk of TLS, AMG 176 lead-in dosing (see Section 6.1.1) will be used and TLS prophylaxis must be initiated in all subjects prior to all lead-in dosing of AMG 176 and prior to all subsequent dose escalations (ie, first dose on the targeted cohort dose level). Prior to administering these doses, all electrolyte values (including potassium, uric acid, phosphorous, calcium, and creatinine) should be reviewed and must be within normal range. However, LDH is not mandatory.

All other protocol-required therapies including, allopurinol, that are commercially available are not provided or reimbursed by Amgen (except if required by local regulation). The investigator will be responsible for obtaining supplies of these protocol-required therapies.

All subjects will be hospitalized to monitor for TLS and all TLS monitoring assessments will be performed as outlined in the Schedule of Activities (see Section 1.3).

The management recommendations below focus on the minimum initial responses required. If a diagnosis of TLS is established, ongoing intensive monitoring and multi-disciplinary management will be conducted per institutional protocols (Coiffier et al, 2008; Cairo et al, 2004).

Tumor lysis syndrome prophylaxis includes:

 Allopurinol or equivalent should be used to reduce uric acid level. This should be initiated at least 72 hours prior to dosing. Treatment may need to be continued for up to 5 weeks. Other agents to reduce uric acid level, such as rasburicase,

Protocol Number: 20200392

Date: 28 April 2022 Page 55 of 149

may be used per principal investigator discretion and the institutional guidelines. Dosing per institutional guidelines.

- Hospitalization and monitoring, beginning the night before AMG 176 administration until at least 24 hours post-first AMG 176 dose.
- IV hydration must be started the night before AMG 176 administration and to be continued until at least 24 hours post—dose during hospitalization as clinically tolerated (refer to Section 11.9.3 for more details about the level of IV hydration required).

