- Monitoring of electrolyte values is required prior to dosing anytime a dose is higher than one previously given to the subject. This will include at the following times:
 - Prior to the week 1, day 1 dose.
 - Prior to each dose during the lead-in period.
 - Prior to the initial dosing at the target dose level.
- Prior to administering these doses, all electrolyte values (including LDH, potassium, uric acid, phosphorus, calcium, and creatinine) must be reviewed and within normal range (samples must be drawn within 24 hours prior to dosing of AMG 176). The investigator's decision to proceed with AMG 176 treatment initiation will be based on these laboratory values.

Within the first 24 hours after either the first dose or dose escalation, if any laboratory criteria for TLS are met, no additional AMG 176 doses should be administered until resolution. A rapidly rising serum potassium is a medical emergency.

Prophylactic dose reductions for potassium, phosphorus and/or uric acid values at the high end of normal range should be considered.

If the potassium, uric acid, inorganic phosphate and/or creatinine values are higher than the normal range or the calcium is lower or higher than the normal range, this (these) value(s) can be approved following a discussion between the Amgen Medical Monitor and investigator.

On the AMG 176 dosing days chemistry labs must be performed pre-dose (within 4 hours before AMG 176 administration), 2, 4, 8, 12, and 24 hours after the start of AMG 176 infusion. Pre-dose labs will be used as baseline to assess potential electrolytes abnormalities occurring post AMG 176 administration. These labs must be reviewed in real time by the investigator.

All 24-hour laboratory assessments may be taken \pm 2 hours, if necessary.

Monitor for signs and symptoms of TLS (eg, fever, chills, tachycardia, nausea, vomiting, diarrhea, diaphoresis, hypotension, muscle aches, weakness, paresthesias, mental status changes, confusion, and seizures). If any clinical features are observed, recheck potassium, phosphorus, uric acid, calcium, and creatinine within 1 hour.

Additional information on the management recommendations of laboratory abnormalities can be found in Section 11.2.

 Nephrology (or acute dialysis service) consultation should be considered on admission (based on investigator discretion) for hospitalized subjects per

Protocol Number: 20200392

Date: 28 April 2022 Page 56 of 149

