11.9.3 Prophylaxis and Management of Tumor Lysis Prophylaxis

The management recommendations below focus on the minimum initial responses required. If a diagnosis of TLS is established, ongoing intensive monitoring and multi-disciplinary management will be conducted per institutional protocols (Coiffier et al, 2008; Cairo et al, 2004).

Tumor lysis syndrome prophylaxis includes:

- Allopurinol or equivalent should be used to reduce uric acid level per SOC. This
 should be initiated at least 72 hours prior to dosing. Treatment may need to be
 continued for up to 5 weeks. Other agents to reduce uric acid level, such as
 rasburicase, may be used per principal investigator discretion and the institutional
 guidelines. Dosing per institutional guidelines.
- All patients should have WBC count less than 25 x 10⁹/L prior to initiation of azacitidine. Cytoreduction prior to treatment may be required.
- Hospitalization and monitoring: beginning the night before AMG 176 administration until at least 24 hours post-first AMG 176 dose.
- Intravenous hydration must be started the night before AMG 176 administration and to be continued until at least 24 hours post—dose during hospitalization as clinically tolerated (see below for more details about the level of IV hydration required)
- Monitoring of electrolyte values is required prior to dosing anytime a dose is higher than one previously given to the subject. This will include at the following times for:

AMG 176:

- Prior to the week 1. day 1 dose
- Prior to each dose during the lead-in period
- Prior to the initial dosing at the target dose level

Azacitidine:

- Pre-dose, 6 to 8 hours after each new dose during ramp-up, and 24 hours after reaching final dose
- Prior to administering these doses, all electrolyte values (including lactate dehydrogenase [LDH], potassium, uric acid, phosphorus, calcium, and creatinine) must be reviewed and within normal range (samples must be drawn within 24 hours

Protocol Number: 20200392

Date: 28 April 2022 Page 135 of 149

prior to dosing of AMG 176). The investigator's decision to proceed with AMG 176 treatment initiation will be based on these laboratory values.

- Within the first 24 hours after either the first dose or dose escalation, if any laboratory criteria for TLS are met, no additional AMG 176 doses should be administered until resolution. A rapidly rising serum potassium is a medical emergency.

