- Prophylactic dose reductions for potassium, phosphorus and/or uric acid values at the high end of normal range should be considered.
- If the potassium, uric acid, inorganic phosphate and/or creatinine values are higher than the normal range or the calcium is lower or higher than the normal range, this (these) value(s) can be approved following a discussion between the Amgen medical monitor and investigator.
- On the AMG 176 dosing days chemistry labs must be performed pre-dose (within 4 hours before AMG 176 administration), 2, 4, 8, 12, and 24 hours after the start of AMG 176 infusion. Pre-dose labs will be used as baseline to assess potential electrolytes abnormalities occurring post AMG 176 administration. These labs must be reviewed in real time by the investigator.
- All 24-hour laboratory assessments may be taken ± 2 hours, if necessary.
- Perform hematology labs at pre-dose (within 4 hours before AMG 176 administration) and 24 hours after the start of AMG 176 infusion.
- Monitor for signs and symptoms of TLS (eg, fever, chills, tachycardia, nausea, vomiting, diarrhea, diaphoresis, hypotension, muscle aches, weakness, paresthesias, mental status changes, confusion, and seizures). If any clinical features are observed, recheck potassium, phosphorus, uric acid, calcium and creatinine within 1 hour.
- Nephrology (or acute dialysis service) consultation should be considered on admission (based on investigator discretion) for hospitalized subjects per institutional guidelines to ensure emergency dialysis is available and the appropriate staff is aware and prepared.

All subjects will receive TLS prophylaxis as described above. Allopurinol or equivalent should be used to reduce uric acid level. This should be initiated at least 72 hours prior to dosing. Treatment may need to be continued for up to 5 weeks. Other agents to reduce uric acid level, such as rasburicase, may be used per investigator discretion and institutional guidelines.

Within the first 24 hours after either the first dose or dose escalation, if any laboratory criteria below are met, no additional AMG 176 doses or azacitidine should be administered until resolution. A rapidly rising serum potassium is a medical emergency.

Nephrology (or other acute dialysis service) should be contacted/consulted (per institutional guidelines to ensure emergency dialysis is available) on admission for any subject hospitalized prophylactically or in response to laboratory changes.

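### The 24-hour tumor lysis hold stops only AMG 176 in two places and both drugs in a third, and none of the three cites its trigger table

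*Protocol*

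**What the plan says.** All three statements cover the first 24 hours after a first dose or a dose escalation.

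- Protocol 6.1.4.1, which applies to all subjects: "if any laboratory criteria for TLS are met, no additional AMG 176 doses should be administered until resolution".
- Protocol 11.9.3, bulleted list: "criteria for TLS are met, no additional AMG 176 doses should be administered until resolution".
- Protocol 11.9.3, the paragraph after that list: "if any laboratory criteria below are met, no additional AMG 176 doses or azacitidine should be administered until resolution".

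Two tables could supply the trigger. Table 11-4 (in 11.9.1) is the Cairo-Bishop definition of laboratory TLS and needs two or more of four changes. Table 11-6 (end of 11.9.3) lists management thresholds row by row. No hold statement cites either.

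Nearby cross-references do not help. Section 11.9.1 sends the reader to Table 1-1, a Schedule of Activities, for laboratory TLS. Section 6.1.4.1 mentions 11.9.3 only for fluids ("refer to Section 11.9.3 for more details about the level of IV hydration required") and points to Section 11.2, the list of laboratory tests, for managing laboratory abnormalities.

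Section 11.9.3 also has a pre-dose check: "all electrolyte values (including lactate dehydrogenase [LDH], potassium, uric acid, phosphorus, calcium, and creatinine) must be reviewed and within normal range". Its list of occasions opens with monitoring "required prior to dosing anytime a dose is higher than one previously given to the subject" and gives the azacitidine times as "Pre-dose, 6 to 8 hours after each new dose during ramp-up, and 24 hours after reaching final dose". Out-of-range potassium, uric acid, phosphate, creatinine or calcium "can be approved following a discussion between the Amgen medical monitor and investigator".

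**The concern.** The difference in drugs matters because of the schedule. In combination treatment, the drug that two of the statements hold is not the next one due. AMG 176 is weekly; azacitidine is daily for the first week. A site working from 6.1.4.1 could record that it had applied the hold and still give azacitidine the next day.

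Section 2.3.2 lists TLS with a fatal outcome among the identified risks of AMG 176 and says the risk may rise with azacitidine. A mandatory rule for that event should read the same wherever it appears and should name its trigger.

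**Working it through.** No sample-size or error-rate figure is involved. The check compares the texts and applies the two tables to illustrative laboratory values.

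**Schedule (Protocol 1.3, dosing footnotes).** AMG 176: days 1, 8, 15, 22. Azacitidine: days 1 to 7. After day 1, the azacitidine doses due before the next AMG 176 dose are days 2 to 7: 7 − 2 + 1 = 6. An AMG 176-only hold that resolves before day 8 therefore withholds no scheduled dose. When a lead-in dose is used, the step up to target falls on day 8, after the cycle 1 azacitidine course, so the exposure is chiefly day 2.

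**Thresholds.** Table 11-4, adults, two or more needed: uric acid at least 8 mg/dL or +25%; potassium at least 6.0 mmol/L or +25%; phosphorus at least 1.45 mmol/L or +25%; calcium at most 1.75 mmol/L or −25%. Table 11-6, relevant rows: potassium up by at least 0.5 mmol/L from the prior value, above the upper limit of normal, or at least 6.0 mmol/L; uric acid at least 8.0 mg/dL; calcium at a 7.0 mg/dL (1.75 mmol/L) threshold together with symptoms; phosphorus at least 5.0 mg/dL (1.615 mmol/L) with a rise of at least 0.5 mg/dL; creatinine up by at least 25%.

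**Cases**, reading the later paragraph as pointing to Table 11-6, the only laboratory thresholds that follow it. The last two columns show the drugs held.

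| Case | Table 11-4 elements | Table 11-6 row met | 6.1.4.1 and bullet | Later paragraph |
|---|---|---|---|---|
| 1. Potassium 6.2 mmol/L and uric acid 8.5 mg/dL | 2 | yes | AMG 176 | both |
| 2. Phosphorus 1.50 and asymptomatic calcium 1.70 mmol/L | 2 | none | AMG 176 | neither |
| 3. Potassium 6.2 mmol/L alone | 1 | yes | none if two elements are needed | both |
| 4. Potassium 4.0 to 4.6 mmol/L | 0 | yes | none | both |
| 5. Creatinine +25% alone | 0 | yes | none | both |

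Case 2: 1.50 × 5.0/1.615 = 4.64 mg/dL, below the 5.0 phosphorus row; 1.70 × 7.0/1.75 = 6.80 mg/dL, and the calcium row needs symptoms whichever way its printed inequality is read.

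Case 4: 0.6/4.0 = 15%, under 25%, and 4.6 is under 6.0; the rise of 0.6 exceeds 0.5, taking the pre-dose value as the prior one.

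**Combining the statements.** In case 1 both drugs are held. In case 2 only AMG 176 is held, although laboratory TLS is established.

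**What else could stop azacitidine in case 2.**

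- Table 6-3 tells the investigator to hold AMG 176, with or without azacitidine, for grade 3 or 4 possibly related non-hematologic events. It leaves azacitidine to judgement, and whether laboratory TLS alone counts as grade 3 here is arguable.
- Once TLS is diagnosed, 11.9.3 defers to institutional management.
- Section 6.2.2 lets investigators interrupt either drug.
- The pre-dose normal-range check is arguable on day 2. Azacitidine is fixed at 75 mg/m² on days 1 to 7, so day 2 is not a higher dose and there is no ramp-up. The check ties sampling to AMG 176 dosing, and exceptions can be approved.
- Section 6.2.2.3, on azacitidine dose changes, has no TLS hold.

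**The case against.** The strongest reply is that nothing conflicts. The AMG 176-only statements are silent on azacitidine; they do not permit it. Section 6.1.4.1 also covers Part 1A, where an AMG 176 hold is complete. Sections 1.3, 2.3.2 and 6.2.2.2.4 send sites to 11.9, where the two-drug statement sits, and applying every statement gives the stricter result. The triggers can be inferred: 11.9.1 adopts Cairo-Bishop and Table 11-4 follows at once, so the reference to Table 1-1 looks like a slip. Subjects are hospitalised and chemistry is reviewed in real time.

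Most of this stands. A reader might infer that the protocol allows azacitidine during TLS, or bars a site from holding it; the text supports neither. The reply does not remove the need to reconcile three unnumbered statements at the bedside, and combining them does not reach case 2.

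It is also tempting to make Table 11-4 the single trigger everywhere. That would weaken protection. With two elements required, case 3 would lose the hold on both drugs that the later paragraph now gives. In cases 4 and 5 the current hold may be stricter than intended, since Table 11-6 itself prescribes rechecks (with fluids for creatinine), but that is a clinical decision.

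**Conclusion.** The concern holds as an unclear mandatory safety instruction. The difference in drugs named is on the page and depends on no reading of any table. The gap in case 2 depends on the later paragraph meaning Table 11-6; if it means Table 11-4, the triggers coincide and only the difference in drugs held remains.

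The scope is combination subjects, chiefly day 2 of cycle 1. The cases show what the tables do and are not frequencies; the documents give none. A reader might also infer that subjects were harmed or that results are affected. Neither is supported. The documents report no such event, and the SAP records early termination (7.1), no enrolment in Part 2 (3.1), and non-investigational product exposure as not applicable (9.6.9). No planned analysis changes. The practical value now lies mainly in correcting the text before it is reused.

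**What to change.** - In 6.1.4.1 and the matching bullet of 11.9.3, extend the hold to azacitidine for combination subjects and cite Table 11-4 as the definition of laboratory TLS.
- In the later paragraph of 11.9.3, keep the hold on both drugs and cite Table 11-6 by number, so that no current hold is lost. Leave any relaxation for the early-warning rows (potassium rise within normal limits, creatinine +25%) to the sponsor's clinicians.
- Correct two pointers: Table 1-1 to Table 11-4 in 11.9.1, and Section 11.2 to Table 11-6 in 6.1.4.1.

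These are wording changes with no added tests and no SAP change. The cost is that some azacitidine doses may be delayed.

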11.9 Appendix 9. Tumor Lysis Syndrome

11.9.1 Cairo-Bishop Tumor Lysis Syndrome Definition and Grading

Common Terminology Criteria for Adverse Events (CTCAE) version 5.0 classifies tumor lysis syndrome (TLS) in grade 3 (present), grade 4 (life threatening consequences; urgent intervention indicated) and grade 5 (death). Presence of TLS is not clearly defined by CTCAE version 5.0. Cairo and Bishop developed a system for defining and grading TLS based on Hande-Garrow classification of laboratory or clinical TLS (Coiffier et al, 2008). For this trial the Cairo-Bishop classification will be used to define presence of TLS, ie, presence of laboratory TLS (see Table 1-1) and clinical TLS (see Table 11-5) including grading as detailed below.

Based on the Cairo and Bishop system, laboratory TLS is present when levels of 2 or more serum values of uric acid, potassium, phosphorus, or calcium are more than or less than normal at presentation or if they change by 25% within 3 days before or 7 days after initiation of treatment (Section 1.3).

Table 11-4. Cairo-Bishop Definition of Laboratory Tumor Lysis Syndrome

| Element | Value | Change from Baseline |
|------------|---|----------------------|
| Uric acid | $\geq 476~\mu mol/L$ or 8 mg/dL | 25% increase |
| Potassium | \geq 6.0 mmol/L or 6 mg/L | 25% increase |
| Phosphorus | \geq 2.1 mmol/L for children or \geq 1.45 mmol/L for adults | 25% increase |
| Calcium | ≤ 1.75 mmol/L | 25% decrease |

Note: Two or more laboratory changes within 3 days before or 7 days after cytotoxic therapy will constitute laboratory tumor lysis syndrome.

Clinical TLS requires the presence of laboratory TLS in addition to 1 or more of the following significant complications: renal insufficiency, cardiac arrhythmias/sudden death, and seizures (Table 11-5). The grade of clinical TLS is defined by the maximal grade of the clinical manifestations as detailed in Table 11-5.

Protocol Number: 20200392

Date: 28 April 2022 Page 133 of 149

Table 11-5. Cairo-Bishop Clinical Tumor Lysis Syndrome Definition and Grading

| Grade | Creatinine ^{a, b} | Cardiac Arrhythmia ^a | Seizure ^a |
|-------|----------------------------|---|--|
| 0 | ≤ 1.5 x ULN | none | none |
| 1 | 1.5 x ULN | intervention not indicated | |
| 2 | > 1.5 – 3.0 x ULN | non urgent medical intervention indicated | one brief, generalized seizure; seizure(s) well controlled by anticonvulsants or infrequent focal motor seizures not interfering with ADL |

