Intravenous (IV) fluids (eg, D5 1/2 normal saline) should be initiated at a rate of at least 1 mL/kg/hr rounded to the nearest 10 mL (target 150 to 200 mL/hr; not < 50 mL/hr).

Protocol Number: 20200392

Date: 28 April 2022 Page 136 of 149

Modification of fluid rate should also be considered for individuals with specific medical needs.

Monitor for symptoms or signs of TLS (eg, fever, chills, tachycardia, nausea, vomiting, diarrhea, diaphoresis, hypotension, muscle aches, weakness, paresthesias, mental status changes, confusion, and seizures). If any clinical features are observed, recheck potassium, phosphorus, uric acid, calcium, and creatinine within 1 hour and perform ECG.

Vital signs should be taken at time of all blood draws or any intervention.

For subjects with risk factors for TLS (eg, circulating blasts, high burden of leukemia involvement in bone marrow, elevated pre-treatment LDH levels, or reduced renal function), consider additional measures, including increased laboratory monitoring and reducing azacitidine starting dose.

The management recommendations below focus on the minimum initial responses required (Roberts et al, 2016). If a diagnosis of TLS is established, ongoing intensive monitoring and multi-disciplinary management will be per institutional protocols.

Protocol Number: 20200392

Date: 28 April 2022 Page 137 of 149

Table 11-6. Tumor Lysis Syndrome Management Recommendations

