Abnormality Management Recommendations Hyperkalemia (including rapidly rising potassium) • Potassium ≥ 0.5 mmol/L • Recheck potassium, phosphorus, uric acid, calcium and creatinine in 1-hour STAT. If further ≥ 0.2 mmol/L increase from prior value (even if potassium within increase in potassium, but still < upper limit of normal normal limits [WNL]) (ULN), manage as per potassium ≥ ULN. Otherwise recheck in 1 hour. • Resume per protocol testing if change in potassium is < 0.2 mmol/L, and potassium < ULN, and no other evidence of tumor lysis. • At discretion of Investigator, may recheck prior to hospitalization. If stable or decreased, and still WNL, hospitalization is at discretion of the Investigator. Potassium phosphorus, uric acid, calcium and creatinine must be rechecked within 24 hours. • Potassium > upper limit of Perform STAT ECG and commence telemetry. normal Nephrology notification with consideration of initiating dialysis. Administer Kayexalate 60 g (or Resonium A 60 g). Administer furosemide 20 mg IV x 1 • Administer calcium gluconate 100 - 200 mg/kg IV slowly if there is ECG/telemetry evidence of life-threatening arrhythmias. • Recheck potassium, phosphorus, uric acid, calcium and creatinine in 1 hour STAT. If potassium < ULN 1 hour later, repeat potassium phosphorus, uric acid, calcium and creatinine 1, 2, and 4 hours, if no other evidence of tumor lysis. • Potassium ≥ 6.0 mmol/L • Perform STAT ECG and commence telemetry. (6.0 mEg/L) and/or • Nephrology (or other acute dialysis service) assessment symptomatic (eg, muscle with consideration of initiating dialysis. cramps, weakness, Administer Kayexalate 60 g (or Resonium A 60 g). paresthesias, nausea, Administer furosemide 20 ma IV x 1. vomiting, diarrhea) Administer insulin 0.1 U/kg IV + D25 2 mL/kg IV. Administer sodium bicarbonate 1 to 2 mEq/kg IV push. If sodium bicarbonate is used, rasburicase should not be used as this may exacerbate calcium phosphate precipitation. Administer calcium gluconate 100 to 200 mg/kg IV slowly if there is ECG/telemetry evidence of life-threatening arrhythmias. Do not administer in same IV line as sodium bicarbonate. Recheck potassium, phosphorus, uric acid, calcium and creatinine every hour STAT.

Page 1 of 3

Protocol Number: 20200392

Date: 28 April 2022 Page 138 of 149

Table 11-6. Tumor Lysis Syndrome Management Recommendations

| Hyperuricemia | |
|--|--|

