| • Uric acid ≥ 8.0 mg/dL (476 μmol/L) | Consider rasburicase (0.2 mg/kg as an intravenous infusion over 30 minutes). |
| | If rasburicase is used, sodium bicarbonate should not be used as this may exacerbate calcium phosphate precipitation. |
| | Recheck potassium, phosphorus, uric acid, calcium and creatinine in 1-hour STAT. |
| • Uric acid ≥ 10 mg/dL (595 μmol/L) | Administer rasburicase (0.2 mg/kg as an intravenous infusion over 30 minutes). |
| OR | When rasburicase is used, sodium bicarbonate should not be used as this may exacerbate calcium phosphate precipitation. |
| • Uric acid ≥ 8.0 mg/dL | Consult nephrology (or other acute dialysis service). |
| (476 μmol/L) with 25% increase and creatinine | Recheck potassium, phosphorus, uric acid, calcium and creatinine in 1-hour STAT. |
| increase ≥ 0.3 mg/dL (≥ 0.027 mmol/L) from pre-dose level | If uric acid < 8.0 mg/dL 1 hour later, repeat potassium, phosphorus, uric acid, calcium and creatinine 2 and 4 hours later, if no other evidence of tumor lysis. |
| Hypocalcemia | |
| • Calcium ≥ 7.0 mg/dL (1.75 mmol/L) | Administer calcium gluconate 50 to 100 mg/kg IV slowly with ECG monitoring. |
| • AND | Telemetry. |
| Patient symptomatic (eg, muscle cramps hypotension, | Recheck potassium phosphorus, uric acid, calcium and creatinine in 1-hour STAT. |
| tetany, cardiac arrhythmias) | If calcium normalized 1 hour later, repeat potassium, phosphorus, uric acid, calcium and creatinine 2 and 4 hours later, if no other evidence of tumor lysis. |
| | Calculate corrected calcium and check ionized calcium if albumin low. |
| Hyperphosphatemia | |
| • Phosphorus ≥ 5.0 mg/dL (1.615 mmol/L) with ≥ 0.5 mg/dL (0.16 mmol/L) | Administer a phosphate binder (eg, aluminum hydroxide, calcium carbonate, sevelamer hydroxide, or lanthanum carbonate). |
| increase | Nephrology (or other acute dialysis service) notification (dialysis required for phosphorus uric ≥ 10 mg/dL). |
| | Recheck potassium, phosphorus, uric acid, calcium and creatinine in 1 hour STAT. |
| | If phosphorus < 5.0 mg/dL 1 hour later, repeat potassium, phosphorus, uric acid, calcium and creatinine 2 and 4 hours later, if no other evidence of tumor lysis. |

Page 2 of 3

Protocol Number: 20200392

Date: 28 April 2022 Page 139 of 149

Table 11-6. Tumor Lysis Syndrome Management Recommendations

| Creatinine | |
|--------------------------------|---|

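### Table 11-6 has the hypocalcemia treatment trigger reversed: IV calcium is tied to calcium at or above 7.0 mg/dL, against the row's own heading and Table 11-4 (minor; check the sign on the page first)

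*Protocol*

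**What the plan says.** Section 11.9.3 introduces Table 11-6 with the statement "The management recommendations below focus on the minimum initial responses required". Under the heading Hypocalcemia, the row combines two conditions with AND:

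- a calcium value, "Calcium ≥ 7.0 mg/dL (1.75 mmol/L");
- symptoms, "Patient symptomatic (eg, muscle cramps hypotension", followed by tetany and cardiac arrhythmias.

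The first action is "Administer calcium gluconate 50 to 100 mg/kg IV slowly with ECG monitoring". Chemistry is then rechecked, and the next step begins "If calcium normalized 1 hour later".

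Section 11.9.1, Table 11-4, gives the calcium criterion for laboratory tumor lysis syndrome (TLS) as "Calcium | ≤ 1.75 mmol/L | 25% decrease".

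**The concern.** The row treats low calcium but is entered by a value at or above the cut-off. Taken literally, it leaves out the symptomatic patients who are truly hypocalcemic and takes in symptomatic patients whose calcium is normal or high.

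The symptom condition does not fully repair this. Hypotension is one of the row's listed symptoms, and Section 11.9.3 also lists it as a general sign of TLS, so it does not point only to low calcium.

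TLS is an identified risk of AMG 176, and Section 2.3.2 records a fatal outcome. A treatment threshold for that risk, in a table presented as the minimum response, should not contradict itself.

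**Working it through.** **Inputs.** The Table 11-6 trigger is ≥ 7.0 mg/dL, printed as 1.75 mmol/L. The Table 11-4 criterion is ≤ 1.75 mmol/L. The molar mass of calcium is taken as 40.078 g/mol.

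**Step 1: are the two cut-offs the same?** mmol/L = mg/dL × 10 / molar mass. For calcium, 7.0 × 10 / 40.078 = 1.747 mmol/L, which is 0.2% below the printed 1.75. Both tables therefore use one cut-off.

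**Step 2: were the digits read correctly?** The same formula was applied to every distinct unit pair on that page of Table 11-6 (× 1000 for μmol/L). Molar masses in g/mol: uric acid 168.11, creatinine 113.12, phosphorus 30.974.

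| Analyte | mg/dL | Computed | Printed | Difference |
|---|---|---|---|---|
| Calcium | 7.0 | 1.747 mmol/L | 1.75 | -0.2% |
| Uric acid | 8.0 | 475.9 μmol/L | 476 | -0.03% |
| Uric acid | 10 | 594.8 μmol/L | 595 | -0.03% |
| Creatinine | 0.3 | 0.0265 mmol/L | 0.027 | -1.8% |
| Phosphorus | 5.0 | 1.614 mmol/L | 1.615 | -0.05% |
| Phosphorus | 0.5 | 0.161 mmol/L | 0.16 | +0.9% |

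All 6 pairs agree within 2%. The digits are sound, so only the sign is in question.

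**Step 3: what does the sign do?** For a symptomatic patient:

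| Calcium, mg/dL | Table 11-6 as it reads (≥ 7.0) | With the sign reversed (≤ 7.0) | Table 11-4 (≤ 1.75 mmol/L) |
|---|---|---|---|
| 6.0 | no | yes | yes |
| 6.5 (1.62 mmol/L) | no | yes | yes |
| 6.9 | no | yes | yes |
| 7.0 | yes | yes | yes |
| 7.5 | yes | no | no |
| 8.0 | yes | no | no |
| 9.5 (2.37 mmol/L) | yes | no | no |
| 11 | yes | no | no |

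The comparison with Table 11-4 is made after rounding to two decimals. As it reads, the row agrees with Table 11-4 only at the boundary. With the sign reversed it agrees at every value tested.

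**Step 4: does anything support ≥?** Nothing does. The heading, the follow-up step and Table 11-4 all require a low value, and no other place in the documents corrects the row.

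**Step 5: how reliable is the sign as read?** That page of Table 11-6 has 9 ≥ signs. Eight are plausible in direction and this one is not. The 6 < signs across the table all point the expected way. The table contains no ≤ sign, so it offers no direct control for a confusion of ≤ with ≥.

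**The case against.** The strongest objection is that everything rests on one machine-read character, and a reading error is not an error in the plan. The first page of the table was clearly read badly: its two columns are interleaved, and one line reads "Administer furosemide 20 ma IV x 1", evidently for mg. The page holding the calcium row also has an oddity, a stray reference to uric acid in the phosphorus dialysis limit. The unit conversions vouch for the digits and say nothing about the sign.

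This stands as a limit on confidence. It does not dispose of the point. The same reading shows ≤ correctly in Table 11-4, and in Section 11.12 it separates ≥ from ≤ on a single line. The calcium row comes from a page read as a structured table, unlike the badly read first page.

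The second objection is that practical harm is unlikely, and most of this is right:

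- The intended direction is obvious to a clinician.
- Section 11.9.3 requires real-time review of chemistry. For any clinical feature it also says "recheck potassium, phosphorus, uric acid, calcium, and creatinine within 1 hour and perform ECG". Established TLS goes to institutional protocols.
- Section 6.7.2 allows any supportive treatment the investigator considers necessary, so a patient below 7.0 mg/dL can be treated regardless of the row.
- The dose-limiting toxicity criterion for clinical TLS (Table 6-2) uses the Cairo-Bishop criteria, whose calcium sign is correct.
- SAP Section 7.1 records early termination, and SAP Section 3.1 notes that Part 2 did not enroll.

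These facts lower the urgency but do not make the row correct.

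**Conclusion.** The concern holds: on the text available, the calcium trigger in Table 11-6 is reversed. It is a minor error, held with medium confidence. The size is one inequality sign at a cut-off of 7.0 mg/dL, with the row and Table 11-4 in opposition on either side of it. No endpoint, stopping boundary, analysis population, sample size or analysis depends on the row. The conclusion assumes that the ≥ sign is printed in the protocol and was not introduced when the PDF was read.

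**What to change.** Look at Table 11-6 on page 138 of 149. If it shows ≥, change the trigger to calcium ≤ 7.0 mg/dL (1.75 mmol/L) in a symptomatic patient, by amendment or site clarification letter. If no subject is still being dosed, a file note and correction before the text is reused would be enough. If the page shows ≤, no change is needed. The cost is one character, with no effect on data, sample size or analysis.
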